1. PRIMARY EFFICACY CRITERION

Evaluation of frequency of any and symptomatic hemorrhagic transformations of ischemic area, detection of intracranial haemorrhages outside the ischemic area. Neuroimaging techniques will be used for evaluation of early and late haemorrhagic transformations in ischemic area and outside. Efficacy endpoint will be assessed in 24 hours, on day 7 and 14 after reperfusion therapy.

2. SECONDARY EFFICACY CRITERIA

The study will use common assessments found to be sensitive to therapeutic effect in NINDS clinical study investigating intravenous administration of rt-PA (Huber, 1999). These include National Institutes of Health Stroke Scale (NIHSS) and modified Rankin scale during hospital follow-up period and on day 90.

In addition, advanced brain imaging will evaluate changes in ischemic area and BBB permeability.

3. CLINICAL STUDY DESIGN

The study is designed to investigate efficacy of cerebrolysin 30 mL for patients with ischemic stroke during IV TLT and standard baseline therapy and early neurorehabilitation.

Therefore, the study design provides for two study groups:

Study group 1 (Cerebrolysin): 30 mL of cerebrolysin in 100.0 mL of 0.9 % NaCl during IVT, baseline therapy, early neurorehabilitation according to standards

Study group 2 (Control): IVT, baseline therapy, early neurorehabilitation according to standards

The clinical study will be carried out in patients with ischemic stroke meeting IVT inclusion and exclusion criteria (Clinical Guideline for Thrombolytic Therapy During Ischemic Stroke (National Clinical Guidelines:

http://193.232.7.120/feml/clinical_ref/0001410674S/HTML/)

The diagnosis of ischemic stroke and its localisation will be determined clinically based on neuroimaging findings (TOAST criteria).

The clinical study stipulates for follow-up period of 90 days, with 4 scheduled visits for clinical assessment at the following time points: screening (at admission), in 24 hours, on day 7, 14, and day 90.

The clinical study is expected to begin in April 2018 (first patient enrollment) and to end (final study report) by September 2020.

The clinical study is expected to be performed from 2018 till 2020.

Patient visits	Screening	Visit 1	Visit 2	Visit 3	Visit 4
Time since treatment initiation	Admission	24 hours after initiation of therapy	Day 7 after treatment initiation	Day 14 after treatment initiation	Day 90 after treatment initiation
Baseline patient information (demographic data, medical history)	+				
Inclusion/exclusion criteria review	+				
Randomisation, number assignment	+				
Non-contrast CT of the brain	+	+	+	+	
CTP* (PS)				+	
MRI* of the brain (DWI, FLAIR, 3D TOF)	+				
MRI* of the brain (DWI, DTI, 3D TOF, ROI)		+			
MRI* of the brain (DTI)				+	
Assessment of neurological impairment using to the NIHSS scale	+	+	+	+	
Assessment of disabilities using the Rankin scale (attachment)	+			+	+
Assessment of vital functions (BP, RR, pulse, T)	+			+	
Haematology	+			+	
Serum biochemistry	+			+	
CRP		+			
ECG	+				
Assessment of the presence and severity of adverse events		+	+	+	

Schedule of the clinical study procedures

* For patients, eligible for advanced brain imaging at the tertiary stroke center.

4. MEASURES TO MINIMISE/PREVENT SYSTEMIC BIAS

Randomisation

Each eligible patient would be randomly assigned into either the Cerebrolysin or control group by simple randomization procedure. One randomization list for all centers would be issued

by generating Bernoulli variates with the probability parameter of 0.333. The Mersenne twister would be used as an active generator and the starting point was set at random.

Allocation instructions would be sealed in opaque envelopes, mixed and distributed between the centers by an independent statistician. Each envelop would be randomly picked by the investigators and would be opened after the subject's recruitment.

Investigators would enroll participants, assign them to the intervention, and assess clinically the primary and secondary endpoints. Imaging data would be evaluated locally by radiologists who would be blinded to the intervention. However, investigators and participants would not be blinded to the treatment assignment because Cerebrolysin has its particular yellowish color and it is impossible to conceal it properly.

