7. WITHDRAWAL CRITERIA

Patients would be withdrawn from further intervention in case neurosurgery is performed or a life-threatening medical (non-neurological) condition occurs. The study would be also discontinued in case of patient's death. The participants have the opportunity to exit the study at any time. The intention-to-treat (ITT) population comprises all recruited patients, subjects completed the study would be included in the per-protocol (PP) analysis. The study ended once the required number of patients would be reached and the protocol would be accomplished by the participants.

Any patient may withdraw from the clinical study without specifying the reason for such decision. If possible, the patient should discuss his/her decision with the investigator. The reasons as well as date and time of withdrawal should be documented in CRF. All the information on the patients deciding to withdraw should be fully documented in CRF until the time of such withdrawal. Where possible, condition of such patients should be monitored for 90 days. Need in final examination (this is a safety visit).

Every effort should be made to make sure the patients randomized remain in the clinical trial for 90 days. This will guarantee that the deviations will not affect the treatment outcome.

Medical conditions developing during the clinical study which are considered as exclusion criteria will require withdrawal of the patient only if clinically needed or at the patient's decision (ITT principle).

The patients withdrawing from the clinical study due to AE will receive therapy in accordance with the current clinical standard, and these patients should be monitored until recovery or stabilisation or until discovery of the plausible cause of the event. All the related information on AE outcome should be documented in CRF.

RANDOMISATION CODES

Preservation of randomisation codes

Patient randomisation codes will be assigned by a person who is not involved in any clinical trial procedures. The envelopes with randomisation codes in each study center will be kept by this person in both electronic and paper format.

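### Investigators who enrol and assess patients pick envelopes in no fixed order, so no check in the protocol can verify adherence to the randomisation list; a second section describes assignment and custody differently

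*Protocol*

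**What the plan says.** The Protocol describes allocation in two places.

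**Clinical Study Design, section 4 (Measures to Minimise/Prevent Systemic Bias), Randomisation.** Patients are "randomly assigned into either the Cerebrolysin or control group by simple randomization procedure". There is a single list: "One randomization list for all centers would be issued", produced "by generating Bernoulli variates with the probability parameter of 0.333". On preparation: "Allocation instructions would be sealed in opaque envelopes, mixed and distributed between the centers by an independent statistician". On use: "Each envelop would be randomly picked by the investigators", with opening once the patient has been recruited. On roles: "Investigators would enroll participants, assign them to the intervention, and assess clinically the primary and secondary endpoints". Investigators and participants know the treatment; the local radiologists who read the images do not. The text gives no order in which envelopes are to be used, no entry on the envelope before it is opened, and no reconciliation of envelopes afterwards.

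**Randomisation Codes, Preservation of randomisation codes (after section 7, Withdrawal Criteria).** Here "Patient randomisation codes will be assigned by a person who is not involved in any clinical trial procedures", and that same person keeps each centre's envelopes, on paper and electronically.

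Two other places bear on the point. The schedule of procedures in section 3 lists randomisation together with number assignment at screening. Section 6 (Studies) requires a registration log of all patients assessed against the inclusion criteria.

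**The concern.** In an open-label trial at eight centres, the allocation procedure is the main protection against selection bias. When envelopes are opened in a fixed order, one particular envelope is due for each patient, and any departure shows as a gap or an inversion. Here no envelope is ever the one that is due. An investigator who opens an envelope and dislikes the result could take another, or could keep the opened one for a later patient. Nothing in the described procedure prevents or records this.

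The person in that position knows the baseline NIHSS score and the admission CT, and later scores the clinical part of the endpoints. If allocation were influenced in this way, a baseline imbalance could not be put down to chance with confidence, and later analysis cannot restore the integrity of the allocation. The second account of who assigns and who keeps envelopes leaves a centre unsure which procedure to follow.

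**Working it through.** The point is procedural and rests on no figure stated in the protocol, so the main check is a comparison of the two sections. Three calculations support it.

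**1. The two accounts side by side**

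| Question | Section 4, Randomisation | Randomisation Codes |
|---|---|---|
| Who assigns? | The investigators | A person outside all trial procedures |
| Who holds the envelopes? | Distributed to the centres; investigators pick | That same person, for each centre |
| In what order are they used? | Random pick | Not stated |
| Is use checked against the list? | Not described | Not described |

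The protocol does not say how an investigator picks freely from envelopes that somebody else keeps.

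**2. Does shuffling and picking bias an honest allocation?** No. The list consists of independent Bernoulli draws with probability 0.333. A random permutation of independent, identically distributed draws has the same distribution. A simulation of 20,000 lists of 264 found a lag-1 covariance of about 0 before and after mixing. What is lost is the order, and with it the means of tying a patient to a list position.

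**3. Would the arm totals reveal redrawing?** The expected number on Cerebrolysin is 264 × 0.333 = 87.9, which agrees with the planned 88. The standard deviation is √(264 × 0.333 × 0.667) = 7.7, so the 95% range is about 73 to 103. A range that wide is a weak check, and in the model below the split does not move at all.

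**4. Illustration of size.** These assumptions are not in the documents:
- Half the patients have a 10% risk of haemorrhagic transformation and half have 30%. The mean is 20%, equal to the control risk in the sample size section.
- Treatment has no effect.
- In a fraction f of patients an unwanted envelope is discarded and one more is drawn, favouring Cerebrolysin for low-risk and control for high-risk patients.

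With allocation probability 1/3, a patient subject to redrawing receives Cerebrolysin with probability 1 − (2/3)² = 5/9 if low-risk and (1/3)² = 1/9 if high-risk. Over all patients:
- P(Cerebrolysin, low-risk) = 1/3 + 2f/9
- P(Cerebrolysin, high-risk) = 1/3 − 2f/9

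The average remains 1/3. The high-risk share becomes 1/2 − f/3 on Cerebrolysin and 1/2 + f/6 on control. The expected risks are therefore:
- Cerebrolysin: 0.10 + 0.20 × (1/2 − f/3) = 0.20 − 0.0667f
- Control: 0.10 + 0.20 × (1/2 + f/6) = 0.20 + 0.0333f

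| f | Cerebrolysin risk | Control risk | Apparent odds ratio |
|---|---|---|---|
| 5% | 19.7% | 20.2% | 0.97 |
| 10% | 19.3% | 20.3% | 0.94 |
| 20% | 18.7% | 20.7% | 0.88 |

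The last line is (0.1867/0.8133) / (0.2067/0.7933) = 0.88. The planned odds ratio is 0.5.

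**The case against.** The strongest reply is that the protocol already has real safeguards: opaque sealed envelopes, preparation by an independent statistician, opening only after recruitment, and simple randomisation without blocks. Together these make the next assignment hard to predict when a patient is enrolled. This stands. The weakness that remains is deliberate redrawing or holding back after an envelope has been opened.

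A reader might infer that the envelopes carry no numbers. The text does not say so: numbering is neither stated nor excluded, the schedule mentions number assignment, and the section on codes speaks of envelopes with codes. Free picking does, however, make any number useless as an order.

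A reader might also infer that shuffling ruins the randomisation, or that tampering could never be found. The permutation argument answers the first. As to the second, a discarded envelope could be exposed by comparing issued, opened and unused envelopes with the enrolled patients and the registration log. But the protocol plans no such comparison, and a held-back envelope that is later used would leave the counts balanced.

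The two accounts of custody can be read together: the uninvolved person may be the independent statistician, keeping an archive copy, since a paper envelope cannot itself be kept electronically. That is possible, but the text does not say it.

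Blinded reading of images protects the detection of haemorrhage. It does not protect against selection before treatment. Finally, the analysis is declared exploratory. This lowers the stakes, but the primary objective is still a randomised comparison.

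**Conclusion.** The concern holds in a limited form. Honest use of the procedure gives a valid allocation with probability 0.333. The defect is that no order of use is fixed, that a second pick or a held-back envelope is not prevented, and that nothing described in the protocol would verify adherence to the list. The two sections on assignment and custody must be reconciled.

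The size of any bias cannot be derived from the documents. Under the assumed 10% and 30% risks with no true effect, redraws in 5% to 20% of patients give an apparent odds ratio of about 0.97 to 0.88. That is a moderate shift in the direction the trial hopes to show, with the arm split unchanged. The documents contain no evidence that redrawing occurred or is planned.

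A reader might infer that steering three or four high-risk patients would produce a large share of the planned effect. The documents do not support this, because it treats every steered patient as a certain haemorrhage. Under the assumed risks, exchanging one high-risk for one low-risk patient moves 0.30 − 0.10 = 0.2 expected events, so moving three to four events takes 3/0.2 = 15 to 4/0.2 = 20 exchanges among 88 patients.

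**What to change.** Amend the Randomisation text in section 4 as follows:
- Keep the Bernoulli list in its generated order. Remove the shuffling step and the random pick.
- Number the opaque envelopes sequentially within each centre.
- Write the patient identifier, date and time on the sealed envelope before it is opened.
- Open envelopes strictly in sequence.
- Reconcile used and unused envelopes against the list and the registration log.

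Then make this section and the section on randomisation codes agree: one statement of who assigns, who holds the envelopes at the centre, and who keeps the master list.

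The cost is a short amendment, renumbering of unused envelopes and some record-keeping at eight centres. Releasing each allocation in real time through one person is not proposed: with treatment starting within 4.5 h of onset, it may need round-the-clock cover that the protocol does not provide.

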5. DESCRIPTION OF THERAPY

Study product

Cerebrolysin

Dosage Form

Cerebrolysin 10 mL/ampule

Study product(s) - Introduction

Cerebrolysin will be administered on a daily basis at a single dose of 30 mL diluted in 0.9 % sodium chloride solution up to 100 mL in a 20-minute intravenous infusion. The control group will not receive cerebrolysin.

The study product will be administered once daily for 14 days starting on the day of baseline assessment.

6. STUDIES

This clinical study will be pilot multicenter clinical trial. The primary endpoint will be testing hypothesis that the patients randomized to the cerebrolysin group will achieve reduced incidence of hemorrhagic transformation compared to the patients randomized to the control group. The secondary endpoints will include overall evaluation of disability and neurological status. Overall number of patients to be enrolled to both groups (1:2 ratio) will be 264.

Eight study centers will recruit patients. The treatment will be initiated within 45-270 min after stroke onset and include 14 daily intravenous infusions. The Cerebrolysin infusions would be associated with the standard baseline and rehabilitation therapy. The result will be assessed at baseline and at three visits, with the final assessment 90 days post stroke.

On admission (the screening), the patients will be evaluated for compliance with inclusion/exclusion criteria. The patients found eligible for the clinical study will be enrolled. The data to be collected at the screening will be provided in table "Schedule of the Clinical Study Procedures". These data include date and time of the stroke, modified Rankin scale rating, evaluation of medicinal products and allergic reactions, collection of medical, neurological history; physical examination, NIHSS rating, evaluation of X-ray findings and evaluation of the results of laboratory tests. Clinical diagnosis of ischemic stroke will be made. Inclusion/exclusion criteria should be further checked. Brain MRI and CT should be made at enrollment and used to rule out hemorrhagic stroke or intracranial tumor. The patients meeting these criteria and providing their informed consent will be enrolled and randomized to the Cerebrolysin group or to the control group.

By the end of the evaluation procedures the patient will receive the first dose of the study product along with thrombolytic therapy.

24-hour monitoring will be performed based on IVT protocol.

Treatment and rehabilitation diary will also be initiated as well as monitoring of adverse events and administration of co-medications.

All patients assessed by inclusion criteria will be entered in the registration log.

The list of baseline evaluations also includes NIHSS rating and modified Rankin scale rating. During the first 24 hours the patients should be monitored based on IVT protocol.

The treatment period will be 14 days. During this period which will always begin 45-270 minutes after stroke onset the patient will receive daily intravenous dose of the study product. The treatment will be assigned by randomization. In 24 hours (visit 1), on days 7 (visit 2), 14 (visit 3) of the treatment period further evaluation procedures will be made according to table "Schedule of the Clinical Study Procedures". Throughout the clinical study all adverse events regardless of their association with cerebrolysin will be collected and recorded in standardised adverse event and serious adverse event forms. Serious adverse events are defined as any medically unfavourable event developing after administration of any dose of the product and resulting in long-term or expressed disability/incapacity. Diagnosis rather than the signs, symptoms and/or other clinical information should be recorded as possible. Severity of each adverse event should be qualified as mild, moderate or severe. The events are evaluated medically including testing and referral to medical specialists. All the current requirements of local regulatory authorities concerning notification of regulatory authorities and local ethics committee on serious adverse events will be followed.

In case a significant adverse event is detected, discontinuation or planned continuation of the study therapy should be discussed immediately. The key factor in this discussion should be the severity of the adverse event and the probability that this adverse event or its exacerbation may be induced by cerebrolysin. The study therapy should be suspended if the patient reports an adverse event which, according to the investigator, may result in discontinuation of further of therapy or if the patient or his/her relatives apply for discontinuation of further therapy.

At the final visit (visit 4, day 90), Rankin scale rating is scheduled.

7. WITHDRAWAL CRITERIA

Patients would be withdrawn from further intervention in case neurosurgery is performed or a life-threatening medical (non-neurological) condition occurs. The study would be also discontinued in case of patient's death. The participants have the opportunity to exit the study at any time. The intention-to-treat (ITT) population comprises all recruited patients, subjects completed the study would be included in the per-protocol (PP) analysis. The study ended once the required number of patients would be reached and the protocol would be accomplished by the participants.

Any patient may withdraw from the clinical study without specifying the reason for such decision. If possible, the patient should discuss his/her decision with the investigator. The reasons as well as date and time of withdrawal should be documented in CRF. All the information on the patients deciding to withdraw should be fully documented in CRF until the time of such withdrawal. Where possible, condition of such patients should be monitored for 90 days. Need in final examination (this is a safety visit).

Every effort should be made to make sure the patients randomized remain in the clinical trial for 90 days. This will guarantee that the deviations will not affect the treatment outcome.

Medical conditions developing during the clinical study which are considered as exclusion criteria will require withdrawal of the patient only if clinically needed or at the patient's decision (ITT principle).

The patients withdrawing from the clinical study due to AE will receive therapy in accordance with the current clinical standard, and these patients should be monitored until recovery or stabilisation or until discovery of the plausible cause of the event. All the related information on AE outcome should be documented in CRF.

RANDOMISATION CODES

Preservation of randomisation codes

Patient randomisation codes will be assigned by a person who is not involved in any clinical trial procedures. The envelopes with randomisation codes in each study center will be kept by this person in both electronic and paper format.

8. SOURCE DATA

The following data will be added directly to CRF and considered as source data:

- vital signs
- data on compliance with thrombolytic therapy criterion including CT scans
- physical examination findings
- efficacy variables including modified Rankin scale, NIHSS scale

Any other data added to CRF (e.g. AEs, medical history, co-medications, laboratory tests, advanced CT and MRI scans, etc.) should be added to primary documents for each patient.

TREATMENT OF PATIENTS

At admission department two cubital peripheral venous catheters should be inserted to left and right arms of the patient. After evaluation of inclusion and exclusion criteria infusion of rt-PA and study product should be initiated.

Dosing of rt-PA will be determined on an individual basis as 0.9 mg/kg body weight, maximum rt-PA is 90 mg. The product will be diluted with water for injections as 50 mg of rt-PA in 50 mL of solvent. 10 % of rt-PA dose will be administered as a bolus intravenous injection within one minute, while the other 90 % dose will be administered intravenously for 60 min (according to patient information leaflet and IVT protocol: Clinical Guidelines for Thrombolytic Therapy During Ischemic Stroke (National Clinical Guidelines).

http://193.232.7.120/feml/clinical ref/0001410674S/HTML/

The study product will be administered simultaneously with rt-PA infusion.

After the completion of rt-PA infusion, the patient should receive standard medication in accordance with the Standard of Medical Care for Patients with Cerebral Infarction (Order of the Ministry of Health of the Russian Federation dated December 29, 2012 No.1740n).

